1.0 What is the condition or intervention to be studied?

The condition to be studied is worsening (flare) of rheumatoid arthritis (RA) in patients who have undergone arthroplasty. RA patients undergoing arthroplasty most often have severe, erosive disease. If the rate of flare approaches the estimated 26% rate suggested in a previous study for RA patients after arthroplasty (*Johnson ACR 2011*), this could be of significance in regards to their long term arthroplasty and disease outcomes. Patients who flare may not be able to participate in the post-operative rehabilitation thought necessary for optimal arthroplasty outcomes, and it may be difficult for patients who flare after

*Please click
Here for
example.*

discontinuing immunosuppressant medications for surgery to regain remission or low disease activity. Detailed clinical data collected longitudinally from RA patients with severe erosive disease undergoing arthroplasty in conjunction with further characterization of the molecular profile of blood and operative tissue could provide valuable information to inform best practices for this patient group.

2.0 What is/are the research question(s)/specific aim(s)? Pose very specific questions that can be addressed within the proposed design of the study. Prioritize them in order of importance.

1. To determine the rate of post-operative RA flare within 6 weeks of surgery, defined as
 - a. Worsening of disease activity, defined as an increase in the DAS-28 by 1.2 or by 0.6 if the DAS28 was ≥ 3.2 , OR
 - b. Patient reported worsening, defined as noting they are worse or much worse on the question rating their RA since pre-surgery
 - c. AND one of:
 - i. patient wants/needs retreatment of DMARDs and/or biologics and/or prednisone increase (or Medrol dose pack or equivalent or intra-articular corticosteroid injection)
 - ii. increase in MD global of 2/10
 - iii. increase in patient global of 2/10 (on the OMERACT Preliminary Flare Questions [PFQ])
 - iv. flare severity score of ≥ 10
2. To evaluate the responsiveness of the OMERACT PFQ in patients who flare, as defined as a worsening of DAS-28 by 1.2 or by 0.6 if the DAS28 was ≥ 3.2 OR by patient reported worsening.
3. To determine predictors of post-operative flare within 6 weeks of surgery such as baseline disease activity measures and biomarkers, including molecules in the Rho associated kinase (ROCK) pathway, which are measures of immune system activation

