3.0 What is/are the hypothesis(es)?

1. 26% of RA patients will flare after TJR, defined as
 - a. Post op increases in DAS28 > 1.2 if baselines < 3.2 or > 0.6 if baseline ≥ 3.2 OR
 - b. Are worse or much worse on question rating their RA since pre-surgery AND
 - c. Have at least one of
 - i. Want / need treatment
 - ii. An increase in MD Global of 2/10
 - iii. An increase in Patient Global of 2/10 (according to the definitions noted above)
2. The OMERACT preliminary flare questions (PFQs) will detect patients who flare as defined above.
3. RA patients who flare after TJR have worse baseline pre-operative disease activity (DAS >3.2), worse baseline function (HOOS, KOOS, HAQ, elbow/shoulder surveys) and more likely will have had a history of withdrawing a biological therapy compared to patients who do not flare.
4. RA patients who flare post op will not meet their physical therapy milestones and will have worse HOOS, KOOS, elbow, or shoulder pain and function outcomes 1 year after arthroplasty.
5. RA patients who flare will exhibit enhanced immune activation when baseline levels are compared to levels in patients who flare within 6 weeks of surgery based on increased expression/activation of ROCK, IRF4, IRF5 and IRF8 and decreased expression/activity of their inhibitors (Def6 and SWAP-70). These molecules participate in a biologic pathway that regulates production of pro-inflammatory cytokines, potential mediators of RA flare.
6. There is a discrete set of genes expressed in circulating monocytes in RA patients during flare and prodrome of flare.

4.0 Identify and define the primary outcome and when the outcome will be measured. If measuring change in post-operative function is the most important, that will be your primary outcome.

The primary outcome is rate of RA flare within 6 weeks of surgery as measured by the OMERACT flare questionnaire.

5.0 Identify and define the secondary outcome(s) and when they will be measured (list additional goals one at a time with their corresponding outcomes).

1. The severity and impact of flares, using the OMERACT PFQs in the post arthroplasty setting: PFQs including flare intensity, duration of flare and worsening of domains associated with flare (pain, fatigue, stiffness, patient

- reported tender and swollen joint count, difficulties with coping and participation).
- 2. DAS28 at baseline and post-op week 6, and the change during this interval.

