- 3. RAPID 3 weekly for 6 weeks and every 3 months for 1 year after arthroplasty, DAS-28, HOOS, KOOS, shoulder/elbow survey, patient global at baseline, 6 weeks, and 1 year.
- 4. Physical therapy functional milestones (PT questionnaire) at baseline and weekly for 86 weeks.
- 5. Biological markers of immune activation including levels of IRF4, IRF5, IRF8, IBP/Def6, SWAP-70, ROCK1, ROCK2 in synovial tissue taken at surgery. Levels of the same immune biomarkers in the peripheral blood measured pre-operatively, at 6 weeks post-operatively and at one year post-operatively.
- 6. Measurement of discrete set of genes expressed in circulating monocytes in RA patients obtained at baseline and weekly for 6 weeks after surgery in a subset of patients at high risk for flare (based on patients who withdrew biologics)

[Help](#)

ID: 2014-233

View: 2.1 Background

[Help](#)

BACKGROUND - Be sure to answer each question individually

1.0 Explain why these research questions are being asked:

RA patients who undergo arthroplasty have severe erosive disease; preliminary data suggests a flare rate as high as 26% in the post-operative period. This study would confirm the rate of post-operative flare, and evaluate the clinical and biologic factors which predict flare. We would also look at the impact of flare on arthroplasty outcomes (HOOS, KOOS, elbow/shoulder survey) and RA disease status (HAQ, DAS-28, RAPID) and better understand the biology of flare.

Flare after arthroplasty is clinically relevant, as medications are typically withheld at the time of surgery with the aim of diminishing surgical site infections.

However, patients who flare may not be able to adhere to post-operative rehabilitation regimens, leading to worse functional outcomes. In addition, patients who flare may have difficulty achieving remission or low disease activity when medications are re-started, leading to worse disease outcomes. There is little information about the characteristics and outcome of flare in the post-operative period. Better understanding of the incidence and clinical characteristics of post-operative flare and the means to predict who will be most likely to flare could lead to more tailored management strategies and potentially better arthroplasty and disease outcomes.

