- Based on data quoted above we have chosen a conservative estimate of flare as 26%.

Ho: within 6 weeks we have a flare rate for RA patients=0.26

Ha: within 6 weeks the flare rate is different from 0.26(=0.1 0.15 0.2)

Power Analysis of One Proportion

Numeric Results for testing H0: P = P0 versus H1: P <> P0

Test Statistic: Exact Test

		Proportion Given H0	Proportion Given H1	Target	
Actual		(P0)	(P1)	Alpha	
Power Alpha	N Beta				
0.8143 0.1857	47	0.2600	0.1000	0.0500	0.0445
0.8036 0.1964	109	0.2600	0.1500	0.0500	0.0387
0.8017 0.1983	394	0.2600	0.2000	0.0500	0.0445

Report Definitions

Power is the probability of rejecting a false null hypothesis. It should be close to one.

N is the size of the sample drawn from the population.

To conserve resources, it should be small.

Alpha is the probability of rejecting a true null hypothesis. It should be small.

Beta is the probability of accepting a false null hypothesis. It should be small.

P0 is the value of the population proportion under the null hypothesis.

P1 is the value of the population proportion under the alternative hypothesis.

Summary Statements

A sample size of 47 achieves 81% power to detect a difference (P1-P0) of -0.1600 using a

two-sided binomial test. The target significance level is 0.0500. The actual significance level

achieved by this test is 0.0445. These results assume that the population proportion under the

null hypothesis is 0.2600.

Power Analysis of One Proportion

Chart Section

We are estimating the rate of the flare rate in RA post-arthroplasty based on previous data. However, if our estimates are wrong, we may be grossly underpowered. Therefore, an interim analysis is planned, when we have collected 25 RA patients to ensure we are adequately powered to detect the primary outcome of flare as previously defined.

- Alpha level: 0.05
- Beta or power level: 0.8 (80%)
- Primary outcome variable estimate (mean +/- s.d. for continuous outcome, frequency/percentage for categorical variable):

The primary outcome is rate of RA flare within 6 weeks of surgery. Since it's a rate, no mean and s.d. are available.

- Number of groups being compared (use 1 for paired analysis within the same subjects):

2 groups: RA – Flare vs. Non-Flare group for secondary outcome.

- Effect size or change expected between groups:

The expected effect size between the flare and non-flare group is 16%, but the interim analysis will be performed after we collect 50 patients.

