- Resulting number per group:

47 with effect size 16% (0.25-0.10) overall.

109 with effect size 11% (0.25-0.15) overall.

394 with effect size 6% (0.25-0.20) overall.

- Total sample size required:

47 patients will provide an adequate sample size to evaluate the primary outcome and enable explorations for the secondary outcomes in this study. It is anticipated that 20% will drop out of the study thus we will need to recruit 57 patients to this study to adequately study the primary and secondary outcomes in this study.

References

Fleiss, J. L., Levin, B., Paik, M.C. 2003. Statistical Methods for Rates and Proportions. Third Edition. John

Wiley & Sons. New York.

Lachin, John M. 2000. Biostatistical Methods. John Wiley & Sons. New York.

Edition. Blackwell Science. Malden, Mass.

Zar, Jerrold H. 1984. Biostatistical Analysis (Second Edition). Prentice-Hall. Englewood Cliffs, New Jersey.

3.0

Data Analysis: describe how the primary outcome will be analyzed and what types of statistical calculations will be used. Do the same for each secondary outcome. Reiterate briefly the main analysis to be done, which groups, which variables, possible confounders. Address how possible confounders will be identified and handled in analysis:

For the Primary Outcome:

Descriptive statistics (rates and proportions, frequency distributions, means, medians, standard deviations and inter-quartile ranges) will be used to describe the baseline data. The two-tailed unpaired Student's t test, or Kruskal-Wallis tests will be performed to evaluate differences in continuous variables between groups (Flare vs. non-Flare group), depending on the distribution of the data, and the Scheffe or Bonferroni multiple comparisons test will be used for multiple comparisons. Chi-Square or Fisher's exact test will be utilized here to compare proportions between groups. Logistic regression will be performed for the HOOS and KOOS score to adjust for potential confounders and effect modifiers.

All secondary outcomes are exploratory.

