Pending the distributions of the data, in aim 2 we will evaluate the standard mean difference or effect size for each domain (WOMAC, DAS-28, Flare questionnaire (pain, Pt global, stiffness, fatigue, coping, participation, Pt reported TJC, SJC) in patients who flare vs. those who do not based on criteria of DAS28 worsening, patient reported worsening, MD global, need to initiate or escalate treatment. We would also explore differences in long term WOMAC scores and biomarkers stratifying by flare and adjusting for unknown confounders including baseline function, age, sex, and co-morbidity score. Standard statistical tests will be used.

In aim 3 we will examine a limited number of predictors of flare within 6 weeks using appropriate statistical methods by using a generalized estimating equation and will adjust for unrecognized confounders/effect modifiers including long term WOMAC scores, baseline function, age, sex, and co-morbidity score, and biomarkers stratifying by flare. Standard statistical tests will be used.

In aim 4 we aim to determine how patients who flare meet physical therapy milestones including walking distance, and ADLs, in comparison to patients who do not flare. The evaluation of meeting physical therapy milestones is exploratory. Physical therapy milestones are routinely evaluated as post-op TJA measures and are done weekly. We will examine the distributions of change for each covariate recorded by physical therapy and compare changes in each domain stratified by flare vs. no-flare.

A potential analytic plan depending on distribution of the final data to assess PT milestones will include:

Physical therapy milestones will be assessed based on the questionnaire and analyzed as outlined below: patient VAS: continuous variable- ranging from 0 ~100, analyzed with T-test or regression

Change will be analyzed by

- 1- ANCOVA and study of change
- 2- GEE and treat delta as our continuous outcome

Walking distance: Ordinal variable - Chi-square, fisher exact

Stairs/Transfers/Activities/Driving/Employed: Nominal- Chi-square, fisher exact

We will also explore whether or not the meeting of PT milestones impacts pain and function at 1 year using the HOOS/KOOS. We will treat PT milestones as a binary and WOMAC outcomes will be analyzed as predictors.

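### The Aim 3 model of flare within 6 weeks adjusts for long-term WOMAC, a score inferred to come after flare and to depend on it, which can bias the predictor estimates

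*Combined protocol and SAP*

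**What the plan says.** All places are in the combined protocol and SAP.

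- **Aim 3** (section 2, item 2.0): "To determine predictors of post-operative flare within 6 weeks of surgery such as baseline disease activity measures and biomarkers".
- **Aim 3 model** (section 2.11.1, item 3.0 Data Analysis): the team will "examine a limited number of predictors of flare within 6 weeks using appropriate statistical methods by using a generalized estimating equation".
- **Aim 3 adjustment set**, from the same paragraph: the analysis "will adjust for unrecognized confounders/effect modifiers including long term WOMAC scores, baseline function, age, sex, and co-morbidity score, and biomarkers stratifying by flare".
- **Aim 2**, in the paragraph just before: "We would also explore differences in long term WOMAC scores and biomarkers stratifying by flare and adjusting for unknown confounders including baseline function". Here long-term WOMAC is an outcome and flare is the grouping variable.
- **Hypothesis 4** (section 2, item 3.0): patients who flare "will have worse HOOS, KOOS, elbow, or shoulder pain and function outcomes 1 year after arthroplasty".
- **Secondary outcomes** (section 2, item 5.0): the schedule includes "DAS-28, HOOS, KOOS, shoulder/elbow survey, patient global at baseline, 6 weeks, and 1 year".
- **Status** (section 2.11.1, item 3.0): "All secondary outcomes are exploratory".

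No other section gives a different Aim 3 model or takes the WOMAC term out of it.

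**The concern.** The same score has two incompatible roles. In Aim 2 it may differ because a patient flared. In Aim 3 it is held fixed as though it could explain why the patient flared. A variable realised after the outcome, and affected by it, is not a confounder. Conditioning on it creates an association between flare and any baseline characteristic that also affects the later score.

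The characteristics most exposed are those the study cares about. Hypothesis 3 proposes worse baseline disease activity and function as features of patients who flare, and both could plausibly affect later joint pain and function. If flare and the predictor both worsen WOMAC, a genuine risk factor is pulled towards or past the null and an irrelevant one looks protective. A larger sample does not remove this. A later score is also unavailable before surgery, when a prediction would be used, and requiring it drops patients who have a 6-week flare result but no later score.

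Section 2.1 (items 3.0 and 4.0) says the predictors found here may be modifiable risk factors and will be candidates for further study. A distorted model could carry the wrong candidates forward.

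**Working it through.** **1. The plan's own figures.** The documents give no calculation for Aim 3. The only one is for the primary outcome: "Ho: within 6 weeks we have a flare rate for RA patients=0.26" against 0.10, two-sided exact binomial test. With at most 0.025 in each tail and N = 47, the test rejects at 6 or fewer or at 19 or more flares. This gives actual alpha 0.0445 and power 0.8143, as stated. The rows for N = 109 (0.0387, 0.8036) and N = 394 (0.0445, 0.8017) also reproduce. None of this depends on the Aim 3 model.

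**2. Does long-term WOMAC come after flare?** No time point is given, and the data collection lists in sections 2.6 and 2.7 name HOOS/KOOS, not WOMAC. The timing is inferred from four things:
- the score is called long term;
- it is listed apart from baseline function;
- Aim 2 compares it between flare groups;
- the Aim 4 analysis text moves from 1-year HOOS/KOOS straight to WOMAC outcomes, and item 5.0 schedules the joint scores at baseline, 6 weeks and 1 year.

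**3. Size of the shift.** Let F be flare (0/1), X a baseline predictor in SD units and W the later score, scaled so that its residual SD is 1 and higher is worse.

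- Flare model: logit P(F=1 | X) = a + bX
- Later score: W = gF·F + gX·X + e, with e ~ N(0,1)

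By Bayes' rule, logit P(F=1 | X, W) = a + bX + gF(W − gX·X) − gF²/2. The coefficient of X after adjusting for W is therefore

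**b − gF·gX**

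Both gF and gX are assumptions; the documents give neither.

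| True OR (b) | gF | gX | gF·gX | OR adjusted for W: formula | Simulated |
|---|---|---|---|---|---|
| 1.00 (0) | 0.5 | 0.3 | 0.15 | exp(−0.15) = 0.86 | 0.86 |
| 1.00 (0) | 0.8 | 0.5 | 0.40 | exp(−0.40) = 0.67 | 0.67 |
| 1.49 (0.4) | 0.5 | 0.3 | 0.15 | exp(0.25) = 1.28 | 1.29 |
| 1.49 (0.4) | 0.8 | 0.5 | 0.40 | exp(0) = 1.00 | 1.00 |

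These simulations used 400,000 patients with intercept −1.15. A second set (8 runs of 20,000, flare rate 26% at the predictor mean) used gF of 0.5 or 1 and gX of 0.3 or 0.5. A true OR of 1.0 became 0.86, 0.79, 0.74 or 0.61, and a true OR of 2.0 became 1.71, 1.57, 1.49 or 1.21. Without W the true value was recovered (0.99 to 1.01 and 1.98 to 2.02). With gF = 0 or gX = 0 there was no shift.

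**4. Shift against sampling error.** With 47 patients and 26% flare, the standard error of a log OR per SD is about 1/√(47 × 0.26 × 0.74) = 0.33. The low-end shift of 0.15 is 0.15/0.33 = 0.45 standard errors; the high-end shift of 0.40 is 0.40/0.33 = 1.2.

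**5. The stratification phrase.** Read literally, every patient in a flare stratum has the same outcome. A logistic fit to such a stratum failed with a singular matrix.

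**6. Patients lost.** Section 2.11.1 expects 20% dropout but does not split it between before and after week 6, so the loss from requiring a later score cannot be computed.

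**The case against.** The strongest reply has four parts.

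**Timing and cause are inferred.** Hypothesis 4 names HOOS, KOOS, elbow and shoulder scores. A reader might infer that the protocol itself says flare worsens WOMAC; it does not say so in those words. This stands as a caveat. The inference is still strong, and no reading of a long-term score listed beside baseline function makes it a pre-flare covariate.

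**The size is assumed.** The simulations contain one predictor and the later score, whereas the plan also adjusts for baseline function, age, sex and co-morbidity. What matters is the predictor's effect on WOMAC given those adjusters. For a biomarker or DAS28 that could be small, and at zero the bias vanishes. This stands: the figures are illustrations. They do not make the term harmless, and it has no offsetting benefit.

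**Stronger charges do not follow.**
- A reader might infer that the model cannot be estimated because it is stratified by flare. The phrase nearly repeats the Aim 2 sentence and may only mean that biomarkers are described by flare group.
- A reader might infer that a GEE has nothing to cluster. Section 2.6 has RA patients answering the flare questions weekly for six weeks, which is a possible cluster. With one record per patient, a logit GEE reduces to logistic regression with robust standard errors. The gap is that the outcome unit is unstated.
- A reader might infer that only about 12 flares (0.26 × 47 = 12.2) must support five adjusters, or 12.2/5 = 2.4 each. That assumes exactly 47 RA patients. The plan recruits 57 (0.26 × 57 = 14.8 before dropout) and allows up to 200 enrolled, with the RA share not given.

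**Aim 3 is exploratory**, and section 2.1 says validation would need a larger study. This lowers the consequence but does not repair the model.

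**Conclusion.** The concern holds in a limited form. As written, the Aim 3 model conditions on a score that is inferred to follow flare and to depend on it. The adjusted log OR is then b − gF·gX instead of b. Under assumed effects of 0.5 to 0.8 SD for flare and 0.3 to 0.5 SD for the predictor, a null OR moves to about 0.86 to 0.67 and a true OR of about 1.5 to between 1.29 and 1.00. The result rests on three assumptions: that long-term WOMAC is recorded after the flare window, that flare affects it, and that the predictor affects it given the other adjusters. If either effect is absent, the bias is zero, though the analysis is still limited to patients with later scores.

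The documents do not support a claim that Aim 3 is certainly not estimable, that a GEE is impossible, or that the primary result is affected. Severity is moderate.

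**What to change.** 1. Delete long-term WOMAC from the Aim 3 adjustment set in section 2.11.1, item 3.0.
2. Restrict Aim 3 covariates to variables measured before surgery. If markers from blood or tissue taken at the operation are wanted as candidate predictors, say so explicitly; they still precede the flare window.
3. Keep long-term WOMAC/HOOS/KOOS only as outcomes. Name the instrument and time point, since WOMAC is not on the collection lists. The closing Aim 4 sentence, which enters WOMAC outcomes as predictors, needs to be brought into line.
4. Remove the stratification by flare from the Aim 3 model, or state that it only means describing biomarkers by flare group.
5. State the outcome unit: GEE if weekly flare status is the outcome, ordinary logistic regression if there is one flare outcome per patient.

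Firth penalization and a cap on the number of adjusters are optional.

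The cost is a wording amendment before analysis. It needs no new data, visits or patients, and it lets every patient with a 6-week flare result and baseline data contribute to Aim 3.

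### Aim 4 gives weekly physical-therapy milestones one-record-per-patient tests without naming the unit of analysis or time point, and names GEE for change without a small-sample correction

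*Combined protocol and SAP*

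**What the plan says.** The analysis of aim 4 is in the Combined protocol and SAP, View 2.11.1, item 3.0 (Data Analysis). It says of the milestones: "Physical therapy milestones are routinely evaluated as post-op TJA measures and are done weekly". It then undertakes to look at the distribution of change in each PT variable and compare changes by flare status.

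The methods named are:

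- **Patient VAS:** t-test or regression.
- **Change:** ANCOVA, or "GEE and treat delta as our continuous outcome".
- **Walking distance (ordinal):** chi-square or Fisher.
- **Five further items:** "Stairs/Transfers/Activities/Driving/Employed: Nominal- Chi-square, fisher exact".

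No unit of analysis, week or per-patient summary is stated. For GEE, no working correlation, variance estimator or small-sample correction is stated. The section calls the evaluation exploratory and the plan a potential one that depends on the final data.

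The number of weekly PT records is unclear. The secondary-outcome list (View 2, item 5.0) prints baseline and weekly for 86 weeks for the PT questionnaire. The same list gives six weeks for the weekly RAPID 3, and View 2.6 gives six weeks for the weekly RA survey.

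**The concern.** The question is longitudinal, but the tests named for six of the milestones take one independent observation per patient. An analyst could apply them to weekly data in three ways, and the plan does not choose between them.

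- **Pooling patient-weeks** counts correlated records as independent patients, so the test loses its level.
- **Testing each week** keeps the level of each test but multiplies the tests.
- **Testing one week** keeps the level, but the week is not named, so it could be chosen after the data are seen. It also discards the trajectory that the section says it will compare.

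GEE would handle the repetition for continuous change. However, its usual sandwich variance is too small when one group has about a dozen patients.

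At stake is hypothesis 4, that patients who flare do not meet their PT milestones. Impaired rehabilitation is also a main reason the Background gives for studying flare.

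**Working it through.** **1. Group sizes.** The plan states "47 patients will provide an adequate sample size to evaluate the primary outcome and enable explorations for the secondary outcomes in this study". Its power table can be reproduced. With N = 47 and P0 = 0.26, the equal-tailed exact binomial test rejects at 6 or fewer or 19 or more flares, with actual alpha 0.0445 and power 0.8143 at P1 = 0.10, as printed. At 26%, 47 × 0.26 = 12.2, so about 12 flare and 35 non-flare patients. At the plan's alternatives of 0.20, 0.15 and 0.10 the flare counts are 9.4, 7.1 and 4.7.

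**2. Assumptions not in the documents.** Six weekly records per patient, exchangeable within-patient correlation ρ of 0.3 to 0.7, and no true difference between groups. Simulations used 20,000 runs per setting unless noted.

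**3. If weekly records are pooled.** 47 × 6 = 282 records would be treated as 282 patients. The design effect is 1 + (6 − 1)ρ, and the approximate rejection rate is 2[1 − Φ(1.96/√design effect)].

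| ρ | Design effect | Formula | Simulated t-test | Simulated chi-square, 50% prevalence |
|---|---|---|---|---|
| 0.3 | 2.5 | 0.215 | 0.215 | 0.163 |
| 0.5 | 3.5 | 0.295 | 0.300 | 0.237 |
| 0.7 | 4.5 | 0.356 | 0.363 | 0.299 |

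The chi-square column is lower because ρ there is on a latent scale. At 50% prevalence a latent 0.3 is an observed correlation of (2/π)·arcsin(0.3) = 0.19, so the design effect is 1 + 5 × 0.194 = 1.97 and the formula gives 0.163. With ρ on the observed binary scale, a beta-binomial simulation (4,000 runs) gives 0.210, 0.299 and 0.359 for chi-square. Across runs and scales the range is about 16% to 37%. More weeks make it worse: at eight weeks the formula gives 0.27, 0.36 and 0.42.

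**4. If each week is tested separately.** Walking distance plus five nominal items over six weeks is 6 × 6 = 36 tests. At the nominal level that is 36 × 0.05 = 1.8 expected false positives. At the simulated single-week rates it is about 1.6 to 1.7 for chi-square (0.043 to 0.046) and 1.0 to 1.5 for Fisher (0.028 to 0.042). For a continuous milestone with t-tests in six weeks, the chance of at least one significant week is 0.239, 0.211 and 0.167 at ρ = 0.3, 0.5 and 0.7.

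**5. If one value per patient is tested.** A single week gives 0.043 to 0.046 (chi-square) and 0.028 to 0.042 (Fisher), so there is no inflation. A t-test on one summary per patient gives 0.049 to 0.051 for continuous outcomes and 0.044 to 0.050 for binary items.

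**6. GEE, continuous outcome.** The ranges at 12 v 35 cover ρ = 0.3 to 0.7; the other rows use ρ = 0.5.

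| Flare v non-flare | Uncorrected sandwich, z | Mancl-DeRouen, t(45) |
|---|---|---|
| 12 v 35 | 0.070–0.074 | 0.048–0.051 |
| 9 v 38 | 0.086 | 0.054 |
| 7 v 40 | 0.103 | 0.061 |
| 5 v 42 | 0.125 | 0.070 |

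A separate 8,000-run check at 5 v 42 gave 0.133 uncorrected. A packaged GEE routine gave 0.075 at 12 v 35 (1,500 runs). For binary items at 12 v 35, uncorrected GEE gives 0.071 to 0.075 at 50% prevalence and 0.083 to 0.085 at 20% or 80%. The corrected version gives 0.050 to 0.052 and about 0.063.

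**The case against.** The strongest reply is that the plan never says patient-weeks are pooled. Its language concerns whether patients meet milestones, and for the one-year analysis it treats the milestones as binary. With one value per patient, chi-square and Fisher are sound. **This stands.** A reader might infer that hypothesis 4 will be supported far too often by chance. The documents do not support that, because the 16% to 37% arises only under pooling.

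A reader might also infer that GEE is itself anticonservative here, or that the VAS intervals will be too narrow. Neither follows. The inflation belongs to an uncorrected variance with a normal reference, the plan names no variance estimator, and ANCOVA is listed ahead of GEE. At the plan's own 26% the excess is about two percentage points. It shrinks with more patients: about 6.8% at 15 v 42 and 5.9% at 26 v 74. Recruitment of 57 is planned.

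Six records is an inference that the printed 86 weeks contradicts. The weekly participant survey in View 2.7 asks about PT attended and missed, not stairs, transfers or driving.

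Item 3.0 also mentions Scheffe or Bonferroni adjustment for flare versus non-flare comparisons. That sentence sits under the primary outcome, and its reach to aim 4 is unclear.

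Finally, the aim is exploratory and the plan only potential. That limits the consequence, but it does not settle the unit of analysis or make chi-square and Fisher suitable for weekly change data.

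**Conclusion.** The point holds in a limited form. For walking distance and the five nominal items, the named tests fit weekly data only if each patient contributes one value, and the plan does not say which value. For continuous change, the one repeated-measures method named lacks the small-sample correction it needs with about 12 flare patients.

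The sizes are conditional. They are about 16% to 37% if records are pooled, up to 36 tests if each week is tested, and about 7% for uncorrected GEE at 12 versus 35. Uncorrected GEE reaches 12% to 13% at 5 versus 42, which is the 10% flare rate used for power. All rest on six weekly records; the pooled and GEE rates also assume exchangeable correlation of 0.3 to 0.7. The primary outcome is unaffected. The effect is confined to secondary, exploratory inference.

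**What to change.** First reconcile the 86 weeks printed for PT milestones with the six-week schedules elsewhere, and state which form records each milestone. Then make the patient the unit of analysis and report one flare test per milestone, by either route:

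- **Patient-level value:** one pre-specified time point or summary per patient, tested by chi-square or Fisher, or by t-test or ANCOVA for VAS. The level is about 5% or below.
- **Repeated-measures model:** one per milestone. Use a linear mixed model with Kenward-Roger degrees of freedom for VAS, and GEE with Mancl-DeRouen variance and a t reference for binary items. Fall back to the patient-level value if cells are sparse or the model does not converge.

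The patient-level route is simpler, and it also serves any item with more than two unordered categories. The mixed model was not simulated here.

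The cost is a few sentences of SAP wording, with no new data. The downside is slightly wider intervals. With very few flare patients or uncommon binary outcomes, the corrected GEE still rejects about 6% to 7% of the time.
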